referred to a primary care physician for further management. Data collection will continue for 1 year or until the time of disease recurrence. Patient's will no longer have data collected after obtaining serum 25(OH)D and leptin levels at the time of recurrence. A retrospective cohort of women with low serum 25(OH)D that did not receive repletion of vitamin D will be used as a control group for comparison. This control group will be identified from available tumor bank serum samples including those previously identified in the above-mentioned unpublished study at the University of Oklahoma. These samples will be used to evaluate serum levels of 25(OH)D, leptin, and evaluate Buffycots VDR SNP polymorphism for *FokI*.

Cohort	Therapy
1 (Normal 25(OH)D)	None
2 (Low 25(OH)D (<20ng/mL)	50,000 IU cholecalciferol weekly for 8 weeks followed by 2,000 IU daily thereafter

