8.0 Study Parameters

8.1 Observations and Tests

The following observations and tests are to be performed and recorded on the appropriate form(s).

Observation and Tests	Screening	At each treatment visit	Completion of primary therapy	6 months after therapy completion	Time of recurrence or 1 year surveillance (if no recurrence)
History & Physical	1	X	X	X	X
Vital Signs and Weight	1				
Toxicity assessment	1	X	X	X	
Serum 25(OH)D	1		X	X	X
Serum Leptin	1		X	X	X

Serum Cr (and GFR)	1				
Red top and Purple topped blood tubes (for VDR SNP analysis)	1				
Serum pregnancy test (if potential exists)	1				

1. Must be obtained within 21 days prior to initiating protocol therapy.

All other blood draws (end of treatment, 6 months after therapy completion, Time of recurrence or 1 year surveillance) must occur within 8 weeks of expected date.

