9.0 Evaluation Criteria

9.1.1 Response Criteria

9.1.1.1 Evaluation of Biomarkers

Clinical Response

If serum 25(OH)D is initially below the lower normal limit, it must normalize ($>20\text{ng/mL}$) for a patient to be considered experiencing a complete response to repletion.

9.1.2 Progression-Free Survival:

Progression-Free Survival (PFS) is defined as the duration of time from start of treatment to time of progression or death, whichever occurs first.

9.1.3 Survival:

Survival is defined as the duration of time from start of treatment to time of death or the date of last contact.

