12.0 Statistical Methods

Upon analysis, patients will be divided into two groups: Vitamin D Deficient Women and Vitamin D Normal Women.

IRB NUMBER: 7488
IRB APPROVAL DATE: 11/23/2021

Outcomes to be analyzed include differences in demographics, clinical, and tumor characteristics between groups, and differences in treatment-related morbidity or mortality between groups, including completion of treatment and treatment delays, and survival. Both 30-day postoperative surgical morbidity and chemotherapy-related morbidity will be assessed. The ability to normalize 25(OH)D levels with oral supplementation in the vitamin D deficient group will be evaluated.

Descriptive statistics will be used to summarize the demographic and clinical characteristics of patients. Chi-square and t-tests will be used to make comparisons between groups. Survival will be estimated with Kaplan-Meier curves and Cox proportional hazards regression. The anticipated enrollment is 100 patients based on estimated new diagnoses of ovarian cancer treated in the Division of Gynecologic Oncology annually at the Stephenson Cancer Center. Based on the previously mentioned unpublished data, we presume that at least 25 of the prospectively enrolled patients will be vitamin D deficient. All of the vitamin D deficient women will be repleted with oral vitamin D. We will compare outcomes between these patients and 75 vitamin D deficient ovarian cancer patients from previous years (these will include patients from the above-mentioned previous retrospective review as well as other patients with banked blood samples) using logistic regression. We will control for age, stage, and histology. With 25 prospective patients and 75 retrospective patients we will have 80% power to detect differences of 32% in chemotherapy delay between ovarian patients who were not vitamin D deficient (33%) and who were vitamin D deficient (65%).

Additionally, the association between serum leptin and 25(OH)D levels will be compared among groups, including any change in leptin levels observed in the vitamin D supplementation group. Because there is a positive linear association between BMI and serum leptin levels, BMI will be corrected for during analysis for potential relationships between serum leptin and 25(OH)D.

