The proportion of patients with VDR *FokI* SNP will be assessed. We will also compare levels of vitamin D at diagnosis, differences in treatment-related morbidity or mortality including completion of treatment, treatment delays, survival and

IRB NUMBER: 7488
IRB APPROVAL DATE: 11/23/2021

response to vitamin D supplementation across 3 SNP allele groups (homozygous mutated, heterozygous mutated, homozygous wild type).

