#### 6. Antitumor Evaluation

1. Treatment related morbidity (including 30-day postoperative surgical morbidity and chemotherapy-related morbidity) will be summarized by descriptive statistics as appropriate and compared across groups (chi-square for categorical variable).
2. Progression-Free Survival (PFS) at end of study (EOS) is defined as the time in months from first dose of the drug to the date of death or the first documented date of progression, whichever comes first. For patients who did not die and did not have progression, the PFS is censored at the last documented tumor assessment.

Survival curve for PFS will be generated using the Kaplan-Meier method. Median PFS with 95% CI will be computed.

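### Prospective follow-up ends at recurrence, but survival to death is still defined and analysed, so deaths after recurrence are missed and overall survival is overstated

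*Protocol*

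**What the plan says.** Protocol 3.0 sets the observation window for prospective patients: "Data collection will continue for 1 year or until the time of disease recurrence". It adds that they "will no longer have data collected after obtaining serum 25(OH)D and leptin levels at the time of recurrence". No exception is made for vital status. In the Protocol 8.1 schedule the last column is "Time of recurrence or 1 year surveillance (if no recurrence"), with nothing after it.

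Protocol 9.1.2 defines PFS as ending at progression or death. Protocol 9.1.3 then defines a second endpoint: "Survival is defined as the duration of time from start of treatment to time of death or the date of last contact".

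Protocol 12.0 lists among its outcomes "differences in treatment-related morbidity or mortality between groups, including completion of treatment and treatment delays, and survival", and says "Survival will be estimated with Kaplan-Meier curves and Cox proportional hazards regression". For the three *FokI* genotype groups it compares "differences in treatment-related morbidity or mortality including completion of treatment, treatment delays, survival and" response to supplementation. SAP 7 repeats that comparison. SAP 6 plans a curve for PFS only: "Survival curve for PFS will be generated using the Kaplan-Meier method". SAP 9 rules out imputation.

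Neither document provides for registry linkage or chart review for deaths after recurrence. Neither says how the 75 historical controls are followed for death.

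**The concern.** The plan analyses an endpoint that its own data rule prevents it from observing. Under 9.1.3, last contact for a woman who recurs is the recurrence blood draw, so she is censored there and only deaths before recurrence are counted. Kaplan-Meier and Cox assume that a censored woman has the same later risk as those who remain under observation. A woman censored because her cancer has returned does not.

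Three uses of survival are exposed, to different degrees:

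- **Survival estimates in prospective women.** These are too high.
- **Repleted women against historical controls.** This is conditional. Protocol 12.0 compares unspecified outcomes with the controls and names logistic regression. If death is one of those outcomes, and control deaths after recurrence are counted, repletion looks better than it is. Logistic regression does not avoid this, because death status is unknown once a woman has recurred. If controls are also cut at recurrence, the false difference goes, but overall survival is invalid in both groups.
- **Genotypes, or deficient against normal prospective women.** A common stopping rule creates no false difference when there is no true one, but it hides any effect on death that acts through recurrence. Bias arises only if the groups mix prospective and retrospective women unevenly.

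**Working it through.** **The plan's own figure.** The only power figure is 80% for chemotherapy delay, 33% against 65%, with 25 and 75 women. Taking two-sided alpha 0.05 (not stated) and placing 33% in the group of 25:

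- pooled rate = (25 × 0.33 + 75 × 0.65)/100 = 0.57
- null SE = √(0.57 × 0.43 × (1/25 + 1/75)) = 0.1143
- alternative SE = √(0.33 × 0.67/25 + 0.65 × 0.35/75) = 0.1090
- z = (0.32 − 1.96 × 0.1143)/0.1090 = 0.88, so power is 81.1%

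The figure reproduces but says nothing about survival. No survival rate, event count or survival power is stated.

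**Model.** Three states (disease-free, recurred, dead), constant hazards, 1-year horizon. All three inputs are assumptions:

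- net 1-year recurrence *r* = 15-40%, λ = −ln(1 − *r*)
- net 1-year death without recurrence *d* = 2-5%, μ0 = −ln(1 − *d*)
- median survival after recurrence *m* = 12-36 months, μ1 = ln 2/(*m*/12)

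**Formulas at 1 year.**

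- Alive and disease-free (PFS): P = exp(−(λ + μ0))
- Alive after recurrence: A = λ/(λ + μ0 − μ1) × (exp(−μ1) − P)
- True survival: P + A
- Kaplan-Meier censored at recurrence tends to exp(−μ0) = 1 − *d*
- Deaths counted: μ0/(λ + μ0) × (1 − P)
- Deaths missed: λ/(λ + μ0) × (1 − P) − A

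**Middle case: *r* = 25%, *d* = 3%, *m* = 24 months.**

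- λ = 0.2877, μ0 = 0.0305, μ1 = 0.3466
- P = 0.7275; A = 0.2063; true survival = 0.9338
- Kaplan-Meier reads 0.9700, an overstatement of 3.6 points
- Deaths counted 0.0261 and missed 0.0401 per woman; share missed = 0.0401/0.0662 = 61%
- Person-years: disease-free (1 − P)/(λ + μ0) = 0.8565; after recurrence 0.0401/μ1 = 0.1156
- Death rate with full follow-up = 0.0662/0.9721 = 0.0681; under the rule it is μ0 = 0.0305; ratio 0.45

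**Selected points and the range over the whole grid (6 × 4 × 5 = 120 combinations).**

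| *r*, *d*, *m* | True 1-year survival | Kaplan-Meier under the rule | Overstatement | Deaths missed per 100 | Death-rate ratio, rule/full |
|---|---|---|---|---|---|
| 15%, 5%, 36 mo | 93.8% | 95.0% | 1.2 points | 1.6 | 0.80 |
| 25%, 3%, 24 mo | 93.4% | 97.0% | 3.6 points | 4.0 | 0.45 |
| 40%, 2%, 12 mo | 86.5% | 98.0% | 11.5 points | 11.9 | 0.14 |
| Whole grid | 84.3-96.5% | 95.0-98.0% | 1.2-11.5 points | 1.6-11.9 | 0.14-0.80 |

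The share of first-year deaths missed is 26-88%. Among 25 repleted women that is 25 × 0.016 = 0.4 to 25 × 0.119 = 3.0 deaths. Simulation with 400,000 patients at the three listed points gave ratios of 0.795, 0.448 and 0.143, in agreement.

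**Historical controls, only if their deaths after recurrence are counted.** With no true effect, the last column is the apparent death-rate ratio. In the middle case 25 × 0.0261 = 0.7 deaths are recorded among repleted women, where equal follow-up would give 25 × 0.0662 = 1.7; the controls show 75 × 0.0662 = 5.0. If a logistic model codes recurring women as alive, the odds ratio is (0.0261/0.9739)/(0.0662/0.9338) = 0.38, with a grid range of 0.10-0.73.

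**Genotype.** Multiplying λ by 1.5 in one group gives a true death-rate ratio of 1.09-1.35 across the grid. Under the rule both groups show μ0, so the ratio reads 1.00.

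**PFS check.** Recurrence ends PFS, so the stop changes nothing. Simulated 1-year PFS (25% recurrence, 2% death without recurrence, 35% 1-year death risk after recurrence; 2,000 runs of 100 patients) was 73.3% both with and without the rule.

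**Sensitivity.** Replacing median survival after recurrence by a 1-year death risk after recurrence of 10-50% gave an overstatement of 0.4 to 11.5 points, in the same direction in every scenario.

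**The case against.** The strongest reply is that no overall survival analysis is really intended. The only survival objective is 1-year DFS, the SAP's abbreviation list has PFS but no overall survival, and SAP 6 plans a curve for PFS alone. On that reading 9.1.3 and the bare word survival in Protocol 12.0 and SAP 7 are leftover wording. This limits the weight of the point but does not remove it: 9.1.3 defines survival separately from PFS, and nothing in 12.0 or SAP 7 says PFS is meant.

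The sizes rest wholly on assumed rates, and 11.5 points is the extreme corner; the grid median is 3.9 points. That stands.

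The control comparison is doubly conditional, and with so few deaths it would say little even with full follow-up. That also stands. In simulated null comparisons with controls followed for 1 year and 2% death without recurrence, a nominal 5% log-rank test rejected in 0.4% of runs (25% recurrence, 35% 1-year death risk after it) and 6.6% (40% and 50%). The harm is a misleading estimate more than a false significant result.

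Finally, a genotype effect acting through recurrence would still show in PFS. True, but the survival comparison in SAP 7 would then report no effect on death where there is one.

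**Conclusion.** The concern holds. The conflict is in the text: observation stops at recurrence, yet survival to death is defined and analysed. The direction of the bias needs one assumption, that the risk of death is higher after recurrence than before it. The size is illustrative only: 1.2 to 11.5 percentage points on 1-year survival under the assumed ranges. Bias against the historical controls arises only if death is compared and control deaths after recurrence are counted.

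The primary 1-year DFS, PFS and the powered outcome of chemotherapy delay are untouched by the stop at recurrence. This should be corrected before analysis, but it does not threaten the primary result.

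**What to change.** Choose one.

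**A. Keep survival to death.** Amend Protocol 3.0 so that vital status and date of death are obtained by chart or registry lookup, without a visit or blood draw, for every prospective woman whether or not she recurs. Use one common cutoff with a stated time origin, and apply the same cutoff and lookup to the historical controls. The origin must be written down: 3.0 gives 1 year without saying from when, and 8.1 places the 1-year visit after the visit 6 months post-therapy. One example is 1 year from start of treatment, for the survival analysis only, leaving planned DFS/PFS follow-up as it is. Cost: a short amendment, possibly a line in the consent form, and one lookup per recurring patient, plus the matching lookup for controls where it is not already done.

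**B. Drop survival to death.** Remove it from Protocol 9.1.3, Protocol 12.0 (both the group and the genotype comparisons) and SAP 7. State that Kaplan-Meier and Cox apply to 1-year DFS/PFS only, which matches SAP 6, and that mortality in those sentences means treatment-related mortality. Cost: wording only.

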4.0 Study Population

4.1 Eligible Patients

4.1.1 The study population will consist of women with newly diagnosed ovarian, fallopian tube, or primary peritoneal cancer and no previous treatment.

4.1.2 A retrospective cohort of women with ovarian, fallopian tube, or primary peritoneal cancer and low serum 25(OH)D that did not receive repletion identified from available tumor bank serum samples.

IRB NUMBER: 7488
IRB APPROVAL DATE: 11/23/2021

4.2 Inclusion Criteria (Prospective patients)

4.2.1 Patients must have a histologic diagnosis of ovarian, fallopian tube, or primary peritoneal carcinoma per pre-treatment biopsies by laparoscopy, or interventional radiology, paracentesis, or CT guided core biopsy. Histologic documentation of the original primary tumor is required via the pathology report.

4.2.2 Patients must have adequate:

4.2.2.1 Renal function: Glomerular Filtration Rate (GFR) ≥ 30 .

4.2.2.2 Gastrointestinal absorption: No underlying malabsorption syndrome (i.e. inflammatory bowel disease, celiac disease).

4.2.2.3 Ability to tolerate oral medication.

4.2.3 Patients taking vitamin D at the time of enrollment without a diagnosis of vitamin D deficiency.

4.2.4 Patients of childbearing potential must have a negative pregnancy test prior to the study entry and be practicing an effective form of contraception. If applicable, patients must discontinue breastfeeding prior to study entry.

4.2.5 Patients must have signed an IRB-approved informed consent and authorization permitting release of personal health information.

4.2.6 Patients must be at least 18 years old.

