3.0 Study Design

This study will contain 2 cohorts, those with normal serum 25(OH)D and those with low serum 25(OH)D at enrollment. The study will take place in women with ovarian, primary peritoneal, and fallopian tube cancer, subsequently referred to as ovarian cancer in this document due to the overlap in disease and treatment.

Patients who have given written consent to enroll in the study will have a serum 25(OH)D drawn in a gold-topped tube (1 to 5mL volume) at time of enrollment and prior to initiation of treatment for their cancer. Serum 25(OH)D levels will be analyzed per laboratory protocol in our University CLIA certified lab. Blood will also be drawn for analysis of serum leptin levels and VDR *FokI* SNP genotype. A purple-topped tube (7 to 10mL volume) and red-topped tube will be collected from prospective patients. The Stephenson Cancer Center Biospecimen Bank will process the red and purple-topped tube into plasma and Buffycoats, label them with a de-identified code and transfer them to [name] lab. The plasma

will be used to evaluate leptin by ELISA and the Buffycoats used to evaluate the *FokI* SNP using PCR. Retrospective serum specimens will be used to measure leptin.

Patients with low serum vitamin D levels, defined as <20 ng/mL, will be provided a supply of cholecalciferol (vitamin D3), 50,000 IU weekly for 8 weeks that will be dispensed in the Stephenson Cancer Center outpatient pharmacy in order to standardize therapy. They will then be provided with a prescription for 2,000 IU of cholecalciferol (vitamin D3) daily following completion of 8 weeks of therapy based on current Endocrine Society guidelines in agreement with U.S. Preventive Services Task Force recommendations [14]. Treatment with cholecalciferol will not impact initiation of treatment for ovarian cancer. Compliance with cholecalciferol repletion will be assessed with medication reconciliation at every gynecologic oncology visit.

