#### **b. Inclusion Criteria**

1. Patients must have a histologic diagnosis of ovarian, fallopian tube, or primary peritoneal carcinoma per pre-treatment biopsies by laparoscopy, or interventional radiology, paracentesis, or CT guided core biopsy. Histologic documentation of the original primary tumor is required via the pathology report.
2. Patients must have adequate:
  1. Renal function: Glomerular Filtration Rate (GFR)  $\geq 30$ .
  2. Gastrointestinal absorption: No underlying malabsorption syndrome (i.e. inflammatory bowel disease, celiac disease)
  3. Ability to tolerate oral medication.
3. Patients taking vitamin D at the time of enrollment without a diagnosis of vitamin D deficiency.
4. Patients with childbearing potential must have a negative pregnancy test prior to the study entry and be practicing an effective form of contraception. If applicable, patients must discontinue breastfeeding prior to study entry.
5. Patients must have signed an IRB-approved informed consent and authorization permitting release of personal health information.
6. Patients must be at least 18 years old.

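### Prospective women need a pre-treatment biopsy diagnosis and tumor-bank controls do not, so the groups may differ in treatment sequence, which no planned analysis takes into account

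*Protocol*

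**What the plan says.** **Entry of prospective women.** Protocol 4.1.1 takes "women with newly diagnosed ovarian, fallopian tube, or primary peritoneal cancer and no previous treatment". Protocol 4.2, which its heading limits to prospective patients, asks in 4.2.1 for a "histologic diagnosis of ovarian, fallopian tube, or primary peritoneal carcinoma per pre-treatment biopsies by laparoscopy, or interventional radiology, paracentesis" or CT-guided core. Section 3.0 has the vitamin D sample drawn "at time of enrollment and prior to initiation of treatment for their cancer".

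**Entry of controls.** Protocol 4.1.2 describes women with the same cancers and "low serum 25(OH)D that did not receive repletion identified from available tumor bank serum samples". It says nothing about how or when the diagnosis was made, or which treatment came first.

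**The SAP version.** SAP 3a lists both the prospective and the retrospective women. SAP 3b, headed only "b. Inclusion Criteria", then repeats the biopsy rule without limiting it to prospective patients.

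**Treatment and analysis.** Protocol 3.0 says that the study collects the treatment course but does not dictate it. The primary objective (Protocol 1.2.1, SAP 1a) covers 30-day surgical morbidity, chemotherapy-related morbidity and 1-year disease-free survival in deficient women with and without repletion. For the logistic regression of 25 prospective against 75 retrospective deficient women, Protocol 12.0 and SAP 2b state: "We will control for age, stage, and histology". SAP section 6, item 1, compares morbidity by chi-square with no adjustment.

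**The concern.** The two groups are not randomised, and they enter through different diagnostic gates. On the literal wording, a woman whose first histology is her cytoreductive specimen cannot enroll prospectively: she has no tissue diagnosis before surgery, and after surgery she is no longer untreated. The same woman can be a control if serum was banked. If women biopsied first are more often given chemotherapy first, the repleted group would hold more of them than the control group.

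Sequence bears on both parts of the morbidity objective. An operation before chemotherapy and one between cycles are different settings for 30-day complications. An operation between cycles also puts a planned gap into the chemotherapy calendar, and neither document says whether such a gap counts as a delay. A difference between repleted and unrepleted women could then partly reflect treatment route rather than vitamin D, or a real effect could be masked.

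**Working it through.** **1. The plan's own power figure.** Inputs from Protocol 12.0 and SAP 2b: n = 25 and 75, delay 33% and 65%. Two-sided alpha of 0.05 is assumed, as the documents state none.

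- Pooled rate: (25 × 0.33 + 75 × 0.65)/100 = 0.57.
- SE under the null: √[0.57 × 0.43 × (1/25 + 1/75)] = 0.1143.
- SE under the alternative: √[0.33 × 0.67/25 + 0.65 × 0.35/75] = 0.1090.
- Power: Φ[(0.32 − 1.96 × 0.1143)/0.1090] = Φ(0.88) = 81.1%.

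The stated 80% is reproduced and is not disputed here.

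**2. What sequence imbalance could do to delay.** The documents give neither the share treated with chemotherapy first nor delay rates by sequence, so the inputs below are assumed. Bias = (share in repleted − share in controls) × (difference in delay risk between sequences). Controls are set at 65%. The false-positive column assumes no vitamin D effect. The power column assumes a true fall to 33% in repleted women.

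| Chemotherapy-first share, repleted / control | Delay-risk gap | Bias | False-positive rate | Power if bias opposes / favors repletion |
|---|---|---|---|---|
| equal | any | 0 | 5% (nominal) | 81% / 81% |
| 60% / 40% | 10 points | 2 points | 5.2–5.5% | 76% / 86% |
| 80% / 40% | 20 points | 8 points | 10.4–11.5% | 56% / 96% |
| 100% / 40% | 30 points | 18 points | 36–38% | 24% / over 99% |

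These figures take no credit for adjustment by age, stage or histology. They describe the unadjusted comparison, or the imbalance that remains after adjustment.

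**3. The same for 30-day surgical morbidity.** With assumed shares of 80% and 30%, and assumed morbidity of 15% after interval and 30% after primary surgery:

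- Repleted: 0.8 × 15 + 0.2 × 30 = 18.0%.
- Controls: 0.3 × 15 + 0.7 × 30 = 25.5%.
- Spurious difference: 7.5 points.

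Shares of 70/40 with morbidity 20/30 give 23 against 26, or 3 points. Shares of 90/20 with 15/30 give 16.5 against 27, or 10.5 points. All three cases assume an imbalance of at least 30 points and lower morbidity after interval surgery. Equal shares give zero, and reversing the two risks reverses the sign.

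**4. What adjustment costs.** With r the correlation between group and sequence, r² = 0.25 × 0.75 × (difference in shares)² / [q(1 − q)], where q is the overall chemotherapy-first share. The standard error grows by about 1/√(1 − r²).

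| Assumed shares | q | r² | SE increase |
|---|---|---|---|
| 70 / 40 | 0.475 | 0.068 | about 4% |
| 80 / 30 | 0.425 | 0.192 | about 11% |
| 90 / 20 | 0.375 | 0.392 | about 28% |

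In power terms, with effective N = 100 × (1 − r²), the scenarios of step 2 fall from 81% to about 80% (60/40), 76% (80/40) and 67% (100/40).

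**5. Room in the model.** Expected delays are 25 × 0.33 + 75 × 0.65 = 57, leaving 43 women without delay. Five parameters (group, age, one each for stage and histology, sequence) leave 43/5 = 8.6 non-events per parameter. Nine parameters (three each for stage and histology) leave 43/9 = 4.8. One more term is affordable only if stage and histology are coded sparingly.

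**The case against.** The strongest reply is that enrichment is an inference. Neither document mentions neoadjuvant chemotherapy or interval surgery, and neither gives the treatment mix of either group. A biopsy by any listed route, laparoscopy included, can also precede primary surgery. Protocol 4.4 wants a population representative of all such patients treated, and accrual is based on the division's annual new diagnoses, so excluding surgery-first women may not have been intended. Adjustment for stage and histology may absorb part of any imbalance. In the mild case of 60/40 and 10 points, the bias is negligible.

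Most of this stands. A reader might infer that the repleted group is in fact enriched for chemotherapy-first patients and that sequence does confound the result. The documents do not support that. Nor do they support the 3 to 10.5 points for surgical morbidity as an estimate, because those inputs leave out a zero imbalance from the start.

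Two further limits are fair. The delay threshold of 7 days or more belongs to the unpublished study in Protocol 2.2, and neither document adopts it for this trial. And since SAP 3b does not say whom it covers, the rule might be meant for controls too. Yet its consent item and its item on vitamin D use at enrollment fit only prospective women, and Protocol 4.2 is explicit about its scope.

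What does not stand is that nothing need be done. Stage and histology need not separate the sequences among women alike on both, and the chi-square uses neither.

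**Conclusion.** The point holds as a possible source of confounding that the plan leaves open. The entry rules differ between the groups, treatment course is left free, and sequence appears in no model, matching, stratification or restriction. It is not shown that the groups do differ in sequence, or which way a bias would run. Under the assumptions above, the shift in delay lies between nil and about 18 points, in either direction, against the 32-point difference the trial is powered for. The plan's power figure is unaffected. The change should be made before analysis because it is cheap and the morbidity comparison is primary and non-randomised.

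**What to change.** - **Record sequence.** Take from the chart, in both groups, whether chemotherapy or surgery came first. The treatment course is already collected for prospective women; for controls it is one more chart item.
- **Name the model.** In Protocol 12.0 and SAP sections 2b and 6, make the adjusted logistic model the analysis for the primary morbidity and delay comparison, not the chi-square alone. Add sequence as one binary covariate and code stage and histology sparingly. Adding the covariate to SAP section 6 as it stands would do nothing, since that section contains no adjusted model.
- **Split surgical morbidity.** Report 30-day morbidity separately for primary and interval operations.
- **Score delay alike.** State how planned surgical gaps are counted, and use the same rule in both cohorts. This is an endpoint rule and changes no care.
- **Sensitivity analysis.** Repeat the comparison with controls restricted to those with a documented pre-treatment tissue or fluid diagnosis.
- **Align the documents.** Make SAP 3b match Protocol 4.2 on whom the biopsy rule covers.

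**Cost.** Beyond the wording and the chart item, the cost is precision: a standard error about 4% larger at assumed shares of 70/40, 11% at 80/30 and up to 28% at 90/20. The loss is greatest where the comparison without sequence is least trustworthy. If the model cannot carry the term, the split tables and the restricted-control analysis remain available.
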